8.3.6.2 Method of Detecting AEs and SAEs

Methods of detecting and recording AE/SAE/AESI/pregnancies, and the assessment of AE/SAE intensity, causality and outcome are provided in [Appendix 4](#).

Open-ended and non-leading verbal questioning of the participants/participants' parents/LARs is the preferred method of acquiring information related to an AE/SAE/AESI/pregnancy.

8.3.6.3 Follow-up of AEs and SAEs

Instructions on follow-up of AEs and SAEs are provided in [Appendix 4](#).

8.3.6.4 Regulatory Reporting Requirements for SAEs

Once an investigator becomes aware that a study participant has experienced an SAE/AESI/pregnancy, he/she must report it to IQVIA within the timeframes provided in [Table 13](#). This is essential for meeting legal obligations and ethical responsibilities for participant safety and the safety of a study intervention under clinical investigation.

For SAEs/AESIs, the investigator will always provide an assessment of causality at the time of the initial report, as defined in the [Appendix 4](#).

Local regulatory requirements and sponsor's policy for the preparation of an investigator safety report for suspected unexpected serious adverse reactions (SUSARs) must be followed. These reports will be forwarded to investigators as necessary.

The sponsor has a legal responsibility to notify local authorities and other regulatory agencies about the safety of a study intervention under clinical investigation. The sponsor

will comply with country-specific regulatory requirements related to safety reporting to the regulatory authority, IRB/IEC, and investigators.

Refer to [Appendix 4](#) for further details regarding the reporting of SAEs/AESIs/pregnancies.

Table 13 Timeframes for Submitting SAEs, Pregnancies, and AESIs

Type of Event	Initial Reports		Follow-up of Relevant Information on a Previous Report	
	Timeframe	Documents	Timeframe	Documents
SAE	24 hours ^{1,2,3}	electronic Expedited AE Report	24 hours ¹	electronic Expedited AE Report
Pregnancy	24 hours ¹	electronic Pregnancy Report	24 hours	electronic Pregnancy Report
AESI	24 hours ^{2,4}	electronic Expedited AE Report	24 hours ¹	electronic Expedited AE Report

AE = adverse event; AESI = adverse event of special interest; SAE = serious adverse event

¹ Timeframe allowed after receipt or awareness of the information by the investigator/study center staff.

² The investigator will be required to confirm review of the SAE/AESI causality by ticking the “reviewed” box in the electronic Expedited AE Report within 72 hours of submission of the SAE/AESI.

³ For coronavirus disease 2019 (COVID-19) related SAEs, reports should be submitted following routine procedures for SAEs.

⁴ Timeframe allowed once the investigator determines that the event meets the protocol definition of an AESI.

8.3.6.5 Treatment of Adverse Events

Any medication administered for the treatment of an SAE/AESI should be recorded in the Expedited AE Report of the participant’s eCRF screen (refer to [Appendix 4](#)).

8.3.6.6 Participant Card

The investigator or investigator’s designee must provide the participant/participant’s parent(s)/LAR(s) with a “participant card” containing information about the clinical study. The participant/participant’s parent(s)/LAR(s) must be instructed to keep the participant card in his/her/their possession at all times throughout the study. In an emergency, this card serves to inform the responsible attending physician/LAR/caregiver/family member that the participant is in a clinical study and that relevant information may be obtained by contacting the investigator.

8.3.7 Treatment of Overdose

8.3.7.1 Vaccine Administration Error

Vaccine administration error is defined as receiving a dose of study vaccine that was not reconstituted as instructed or administered by a different route from the intended route of administration.

Any vaccine administration error detailed in this protocol must be reported as an AE, and if overdose is associated with an SAE, it must be reported as such within 24 hours to IQVIA.

8.3.7.2 Overdose of Study Vaccine

An overdose of study vaccine (whether accidental or intentional) is defined when a dosage higher than the recommended dosage is administered in 1 dose of study vaccine MenABCWY and/or MenB and/or MenACWY.

An overdose would also occur if 2 doses of the study vaccine are administered within 2 weeks of the recommended interval between doses.

Any overdose of study vaccine detailed in this protocol must be reported as an AE, and if overdose is associated with an SAE, it must be reported as such within 24 hours to the sponsor's designee.

8.3.8 Medical Device Deficiencies

The study interventions (MenABCWY and *Bexsero*) are combination products constituted of a device and biologic product (e.g., pre-filled syringes). Refer to [Appendix 1](#) for the definition of a combination product and a medical device deficiency.

8.3.8.1 Detection, Follow-up and Prompt Reporting of Medical Device Deficiency

The investigator is responsible for the detection, documentation and prompt reporting of any medical device deficiency occurring during the study to the sponsor's designee. This applies to any medical device provided for the conduct of the study.

Device deficiencies will be reported to the sponsor's designee within 24 hours after the investigator determines that the event meets the protocol definition of a device deficiency. Refer to [Appendix 4](#) for definitions and details on recording and reporting of these events.

The investigator will ensure that follow-up includes any additional investigations to elucidate the nature and/or causality of the deficiency. Follow-up applies to all participants, including those who discontinue study intervention or the study.

New or updated information will be recorded on the originally completed form with all changes signed and dated by the investigator and reported to the sponsor's designee within 24 hours.

8.3.8.2 Regulatory Reporting of Medical Device Deficiency When Used as Combination Product

The investigator will promptly report all device deficiencies occurring with any medical device provided for use in the study in order for the sponsor to fulfill the legal responsibility to notify appropriate regulatory authorities and other entities about certain safety information relating to medical devices being used in clinical studies. Refer to [Appendix 4](#) for details of reporting.

The investigator, or responsible person according to local requirements (e.g., the head of the medical institution), will comply with the applicable local regulatory requirements relating to the reporting of device deficiencies to the IRB/IEC.

8.4 Pharmacokinetics

Pharmacokinetic parameters will not be evaluated in this study.

8.5 Pharmacodynamics

Pharmacodynamic parameters will not be evaluated in this study.

8.6 Genetics

No samples will be collected during this study for genetic or pharmacogenetic research.

8.7 Biomarkers

No biomarkers will be collected for pharmacogenetic research in this study.

8.8 Health Outcomes

No economic health outcome measures will be collected in this study.

8.9 Study Procedures During Special Circumstances

During special circumstances (e.g., coronavirus disease 2019 [COVID-19] pandemic), the specific guidance from local public health and other competent authorities regarding the protection of individuals' welfare must be applied. For the duration of such special circumstances, the following measures may be implemented for enrolled participants:

- Safety follow-up may be made by a telephone call, other means of virtual contact or home visit, if appropriate.

- If an eDiary device was provided to the participant, it may be returned to the study center by conventional mail after the end of the relevant data collection period.
- Visits for suspected AEs may take place in a different location* other than the study center or at participant's home. If this is not feasible, then the medical evaluation of AEs may take place virtually with documentation of symptoms by other means of communication (e.g., phone call or videoconference), if possible.
- Biological samples may be collected at a different location* other than the study center or at participant's home. Biological samples should not be collected if they cannot be processed in a timely manner or appropriately stored until the intended use.

**Note: It is the investigator's responsibility to identify an alternate location. The investigator should ensure that this alternate location meets ICH Good Clinical Practice (GCP) requirements, such as adequate facilities to perform study procedures, appropriate training of the staff and documented delegation of responsibilities in this location. This alternate location should be covered by proper insurance for the conduct of study on participants by investigator and study center staff other than the designated study center. Refer to EMA Guidance on the Management of Clinical Trials during the COVID-19 pandemic (version 2, 27 March, 2020) for more details.*

Impact on the per protocol set (PPS) for immunogenicity will be determined on a case by case basis.

9.0 STATISTICAL CONSIDERATIONS

9.1 Statistical Hypotheses

The following study hypotheses are ordered into 2 families that will be tested in a fixed sequential design with full alpha propagation. Family 1 will be tested first and family 2 will only be tested if the hypothesis in family one is successfully demonstrated.

First Co-Primary Immunogenicity Objective (Family 1)

The first co-primary immunogenicity objective is to demonstrate the immunological non-inferiority (NI) of the antibody response to MenABCWY vaccine, compared to MenACWY vaccine given to healthy participants, previously primed with MenACWY, as measured by percentage of participants with 4-fold rise in hSBA titer against each of the *N. meningitidis* serogroups A, C, W, and Y, at 1 month after the second MenABCWY vaccination and 1 month after the MenACWY vaccination (single dose). This translates to the following hypotheses:

$$H_0: (p1_MenABCWY_{(i)} - p1_MenACWY_{(i)}) \leq -10\%$$

vs.

$$H_1: (p1_MenABCWY_{(i)} - p1_MenACWY_{(i)}) > -10\%$$

Where $p1_MenABCWY_{(i)}$ denotes the percentages of participants with 4-fold rise in hSBA titers for serogroups $i=A, C, W,$ and $Y,$ 1 month after the second vaccination of MenABCWY group and $p1_MenACWY_{(i)}$ denotes the percentages of participants with 4-fold rise in hSBA titers for serogroups $i=A, C, W,$ and $Y,$ 1 month after the single vaccination of MenACWY group.

NI criterion: Non-inferiority will be demonstrated if the lower limit of the two-sided 95% CI for the percent difference in the 4-fold rise in hSBA titers ($p_MenABCWY - p_MenACWY$) is above -10% for each serogroup A, C, W, and Y.

Second Co-Primary Immunogenicity Objective (Family 2)

The second co-primary immunogenicity objective is to demonstrate the immunological NI of the antibody response to MenABCWY vaccine, compared to MenACWY vaccine given to healthy participants, previously primed with MenACWY, as measured by percentage of participants with 4-fold rise in hSBA titer against each of the *N. meningitidis* serogroups A, C, W, and Y, at 1 month after the first MenABCWY vaccination and 1 month after the MenACWY vaccination (single dose). This translates to the following hypotheses:

$$H_0: (p2_MenABCWY_{(i)} - p2_MenACWY_{(i)}) \leq -10\%$$

vs.

$$H_1: (p2_MenABCWY(i) - p2_MenACWY(i)) > -10\%$$

Where $p2_MenABCWY(i)$ denotes the percentages of participants with 4-fold rise in hSBA titers for serogroups $i=A, C, W,$ and $Y,$ 1 month after the first vaccination of MenABCWY group and $p2_MenACWY(i)$ denotes the percentages of participants with 4-fold rise in hSBA titers for serogroups $i=A, C, W,$ and $Y,$ 1 month after the single vaccination of MenACWY group.

NI criterion: Non-inferiority will be demonstrated if the lower limit of the two-sided 95% CI for the percent difference in the 4-fold rise in hSBA titers ($p_MenABCWY - p_MenACWY$) is above -10% for each serogroup A, C, W, and Y.

9.2 Sample Size Determination

The sample size calculation was based on data from the MenABCWY, V102_03E1 study after adjusting for the variabilities due to different settings of the study (e.g., differences in population, differences in antibody assays, and different strain for serogroup A) (Table 14).

Assuming that MenACWY group will induce a 4-fold rise in about 95% of the participants for each of the 4 serogroups; MenABCWY will induce a 4-fold rise in about 91% of the participants for A and W serogroups, and 93% of the participants for C and Y serogroups; and using a 1-sided score test (Miettinen, 1985), non-inferiority margin of -10% and actual margins as given in Table 14, an estimated number of evaluable participants ($n=542$) and individual powers of 96.00%, 99.95%, 96.00%, and 99.95% for each A, C, W, and Y serogroup test, will give a global power of 90% to demonstrate NI of MenABCWY vs MenACWY.

Family 1: Assuming that MenABCWY and MenACWY groups will induce a 4-fold rise in about 95% of the participants for each of the 4 serogroups (Table 14), and using a 1-sided score test (Miettinen, 1985), non-inferiority margin of -10% and actual margin of 0%, an estimated number of evaluable participants ($n = 225$) and individual powers of 99.87% for each A, C, W, and Y serogroup test, will give a global power of 99.48% to demonstrate non-inferiority of MenABCWY versus MenACWY.

Family 2: Assuming that MenACWY group will induce a 4-fold rise in about 95% of the participants for each of the 4 serogroups; MenABCWY will induce a 4-fold rise in about 91% of the participants for A and W serogroups, and 93% of the participants for C and Y serogroups; and, using a 1-sided score test (Miettinen, 1985), non-inferiority margin of -10% and actual margins as given in Table 14, an estimated evaluable participants ($n=542$) and individual powers of 96.00%, 99.95%, 96.00%, and 99.95% for each A, C, W, and Y serogroup test, will give a global power of 91% to demonstrate NI of MenABCWY versus MenACWY.

For the multiplicity adjustment, all hypotheses will be ranked into two families according to the following power of test:

Table 14 Power to Demonstrate Immunological Non-inferiority for Serogroups A, C, W, and Y of MenABCWY Compared to MenACWY (Primary)

Serogroup	4-fold rate	4-fold rate MenABCWY	NI margin	Actual margin	Power	N
	MenACWY					ABCWY/ ACWY
Family 1: NI, 2-sided score test (Miettinen and Nurminen, 1985)						
A	95%	95%	-10%	0%	99.87%	225
C	95%	95%	-10%	0%	99.87%	225
W	95%	95%	-10%	0%	99.87%	225
Y	95%	95%	-10%	0%	99.87%	225
Global Power					99.48%	
Family 2: NI, 2-sided score test (Miettinen and Nurminen, 1985)						
A	95%	91%	-10%	-4%	96.00%	542
C	95%	93%	-10%	-2%	99.95%	542
W	95%	91%	-10%	-4%	96.00%	542
Y	95%	93%	-10%	-2%	99.95%	542
Global Power					91.00%	

n = number of participants; NI = non-inferiority

Considering that approximately 10% of the selected participants might withdraw or not be evaluable for the immunogenicity objectives, the target sample size to be analyzed will be 270 participants per group and 603 participants per group for the first co-primary and the second co-primary objectives, respectively.

Evaluable means all participants included in the set for the statistical analysis defined in Section 9.3. The sample size calculation was performed in PASS 12 (Hintze, 2013). The global power for all 4 strains across Family 1 and Family 2 is the product of individual powers.

Approximately 1206 participants will be randomized in a 1:1 ratio to achieve 1084 evaluable participants (542 per group).

Withdrawals will not be replaced.

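### Protocol 9.2 gives Family 2 global power as both 90% and 91% for identical assumptions, and neither is the product of the stated individual powers (92.1%)

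*Protocol*

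**What the plan says.** Protocol 9.2 opens its power statement with a paragraph that carries no family label. It assumes that the "MenACWY group will induce a 4-fold rise in about 95% of the participants for each of the 4 serogroups", with MenABCWY at 91% for A and W and 93% for C and Y. It cites a one-sided score test, a margin of -10%, n=542 and individual powers of 96.00%, 99.95%, 96.00% and 99.95%, and concludes that these "will give a global power of 90% to demonstrate NI of MenABCWY vs MenACWY".

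Two paragraphs later, under the label Family 2, the same rates, test, margin, n and individual powers are listed again. This time they "will give a global power of 91% to demonstrate NI of MenABCWY versus MenACWY". Table 14 prints 91.00% as the global power at the foot of its Family 2 block. Its Family 1 block has its own global power, 99.48%, from four individual powers of 99.87%.

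Below Table 14 comes the rule: "The global power for all 4 strains across Family 1 and Family 2 is the product of individual powers".

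SAP 7.4 refers the reader back to Protocol 9.2 and gives no power figure of its own.

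**The concern.** One set of inputs cannot produce two global powers, and the protocol states a rule by which a reader can check both. Neither 90% nor 91.00% satisfies it. The wording of the rule also leaves it unclear whether global power means all four serogroups within one family or all eight tests across both.

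Family 2 is the objective that requires 542 evaluable participants per group, and hence 1206 randomized. Because Family 2 is tested only if Family 1 succeeds, the chance of meeting both objectives is a figure a reader will look for, and no number in 9.2 is labelled as that. At stake is whether the design's headline power can be traced. Whether the trial is large enough for Family 2 is not in doubt.

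**Working it through.** **Inputs.** All are from Protocol 9.2 and Table 14 except alpha. Section 9.2 does not state alpha. Protocol 9.1 bases the decision on the "lower limit of the two-sided 95% CI for the percent difference in the 4-fold rise in hSBA titers", which implies one-sided 2.5%.

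**1. The plan's Family 1 figure, from its own inputs.** 0.9987⁴ = 0.9948, which is the printed 99.48%. So for Family 1 the product is taken within the family.

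**2. The same rule for Family 2.** 0.96 × 0.9995 × 0.96 × 0.9995 = 0.9207, or 92.1%. The 90% is 2.07 points low and the 91% is 1.07 points low.

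**3. Are the individual Family 2 powers right?** The asymptotic score-test power is

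Φ{(pT − pC + 0.10 − 1.96·s₀)/s₁},

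where s₁ uses the assumed rates and s₀ uses the rates restricted to a difference of −0.10.

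- A and W (91% vs 95%, 542 vs 542): restricted rates 0.8637 and 0.9637, s₀ = 0.01678, s₁ = 0.01545. z = (0.06 − 1.96 × 0.01678)/0.01545 = 1.754, so power is 96.03%.
- C and Y (93% vs 95%, 542 vs 542): restricted rates 0.8673 and 0.9673, s₀ = 0.01646, s₁ = 0.01441. z = (0.08 − 1.96 × 0.01646)/0.01441 = 3.313, so power is 99.95%.

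Both agree with Table 14 and their product is 92.1%. Exact binomial enumeration gives 96.20% and 99.96%, product 92.5%. The individual powers are sound, and only the global figure is off.

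**4. Could rounding explain it?** With the printed two-decimal inputs, the product lies between 92.06% and 92.08%. Even if 96.00% stood for 95.5%, it would be (0.955 × 0.9995)² = 91.1%, still above the printed 91.00%.

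**5. Could correlation between serogroups explain it?** Under any dependence, the chance that all four tests succeed is at least 1 − (0.04 + 0.0005 + 0.04 + 0.0005) = 91.9%. Both 90% and 91.00% fall below that floor.

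**6. The product across both families.** From the stated inputs, 0.9948 × 0.9207 = 0.9159, or 91.6%. The floor under any dependence is 1 − 4 × 0.0013 − 0.081 = 91.4%. Again neither 90% nor 91.00% fits.

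**7. How firm is a joint figure?** It depends on Family 1's 99.87%, checked with the same formula at 95% vs 95%:

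| Family 1 n (ABCWY vs ACWY) | s₀ | s₁ | z | Power per test | Family 1, four tests | Joint with Family 2 (0.9214) |
|---|---|---|---|---|---|---|
| 225 vs 542 | 0.02447 | 0.01728 | 3.01 | 99.87% | 99.48% | 91.7% |
| 225 vs 225 | 0.02509 | 0.02055 | 2.47 | 99.33% | 97.3% | 89.7% |

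The stated 99.87% reproduces only with 225 vs 542. Table 14 lists a single 225 under a column headed for both groups. The 91.6% in step 6 and the 91.7% here differ only because step 6 uses the printed, rounded powers.

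**The case against.** The strongest reply is that the rule refers to both families. On that reading the relevant product is 91.6%, and 91.00% would be a truncated joint figure placed in the wrong block of the table. The amendment history lends this some support as to origin: the superseded single-objective table carried a global power of 92.00%, and 0.9948 × 0.92 = 91.5%. What stands is that the scope of the rule is ambiguous and that this may be where 91% came from. It does not rescue the figure. The text attaches 91% to Family 2, Table 14 sets it against a separate Family 1 value, and 91.00% is not 91.6%.

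A reader might also infer that the 90% is the joint power with 225 per group in Family 1, since 89.7% rounds to 90%. The documents do not support this. That paragraph cites only n=542 and the four Family 2 powers, and 225 per group contradicts the 99.48% printed for Family 1. Nor does the wording present 90% as a design target: it says the inputs will give it.

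A further objection is that the matter is small. That is correct. Both figures err on the conservative side for Family 2 and nothing operational depends on them.

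Finally, one could ask the sponsor simply to print 91.6% as the joint power. That would be premature, because it takes Family 1's 99.87% on trust while the n behind it is unclear. Table 11's footnote makes 225 vs 542 plausible: controls are all tested at Day 31, and about 250 ABCWY samples are tested at Day 211 (250 × 0.9 = 225). But 9.2 and Table 14 do not say so.

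**Conclusion.** The inconsistency is real. Family 2 global power is given as 90% and as 91% for the same inputs. By the product rule that reproduces Family 1's own figure, it should be 92.1%. Read across both families, the stated inputs give 91.6%, so neither printed figure is right on either reading.

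The size is 1 to 2 points, in the conservative direction. The 92.1% assumes one-sided 2.5%, 542 per group, the rates in 9.2, and independence between serogroups as the product rule implies. The 91.9% floor needs no independence.

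A reader might infer that Family 2 is underpowered or that 1206 is wrong. The documents do not support that: the individual powers reproduce, and correcting the global figure raises it. The joint power over both families cannot be settled from 9.2 as written, since it is about 91.7% or about 89.7% depending on Family 1's n per arm. This is a consistency correction, and no decision rule changes.

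**What to change.** In Protocol 9.2:

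1. Delete the unlabelled paragraph that ends in 90%, since it duplicates the Family 2 paragraph.
2. Change Family 2 global power to 92.1% in the text and in Table 14.
3. Reword the sentence under Table 14 to say whether global power is the product within a family or across both.
4. If a joint figure is wanted, first state Family 1's n for each arm, rerun the Family 1 powers at that n, and then print the joint figure on its own labelled line. Expect about 91.7% with 225 vs 542, or about 89.7% with 225 per group. In the second case, Family 1's 99.87% and 99.48% must change as well, to about 99.3% and 97.3%.

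Items 1 to 3 change one paragraph, two figures and one sentence. Item 4 adds one line and a short rerun. Enrolment, analysis and decision criteria stay as they are.

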9.3 Populations for Analyses

Populations for analyses in this study are defined in [Table 15](#).

Table 15 Populations for Analyses

Analysis set	Description
Enrolled Set (Enr)	Participant who agreed/participant for whom parent(s)/LAR(s) agreed to participate in a clinical study after completion of the informed consent process and randomized or received study intervention or undergone an invasive procedure.
Exposed Set (ES)	All participants who received at least 1 dose of the study intervention. The allocation in a group is done in function of all administered interventions.
Full Analysis Set (FAS)	All participant who received at least 1 dose of the study intervention and have post-vaccination immunogenicity data
Per Protocol Set (PPS)	All participants who received at least 1 dose of the study intervention to which they are randomized and have post-vaccination data (FAS) minus participants with protocol deviations that lead to exclusion from the PPS.
Unsolicited Safety Set (USS)	All participants who received at least 1 dose of the study intervention (ES) that report unsolicited AEs/report not having unsolicited AEs
Solicited Safety Set (SSS)	All participants who received at least 1 dose of the study intervention (ES) that report solicited safety data

AE = adverse event; LAR = legally acceptable representative

